# two groups, treatment and WL control.
# they start off with distributions with the same mean and sd (due to randomisation)
# the WL control stays the same, the treatment group changes to arrive at a d = 0.4, which i
# what investigators stipulated in advance
# the shape of the change should not matter that much for this linear model calculation

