- T3: 12 weeks (after the start of the intervention for the active group or the entry into the study for the WL group)

The secondary outcomes will be measured at time points 0 (T4) and 12 weeks (T5) for both AG and WL.

Model

The investigators will follow standard practice for RCTs and apply an ANCOVA model to estimate the effects of treatment. The formalism is:

y ~ b0 + b1xtreatment_group + b2xtime + b3xtreatment_groupxtime + covariates (1)

Where, y is each outcome, b1-b3 are the regression coefficients and covariates denote covariates at randomisation (DETERMINE)

The inference of interest for the model concerns b3, the interaction term, as the investigators posit that there will be a difference in slopes between the treatment groups.

The inference is going to happen via an estimation of the t-statistic, defined as follows"

t = b3/SE(2)

Where SE is the standard error for coefficient b3

[figure not shown]
t > 1.96(3)

And 1.96 is the critical value for statistical significance at alpha = 0.05.

Target Sample Size per Arm

Parameters:

- power = 0.8
- alpha = 0.05
- Correlation between time points = 0.6 (a conservative estimate based on https://www.ncbi.nlm.nih.gov/pmc/articles/PMC2222612/)
- Effect size corresponding to d = 0.5

library(tidyverse) # for data wrangling library(faux) # for simulation

library(broom) # for tidy analysis results

set.seed(1974)

I will simulate the following

```

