# c) number of people, sample size, which I will vary for the simulation
# here comes the actual function
ancova sim func <- function(df means, sd across, n subjects, number sims,
correlations across){
 arts on pres sim <- sim design(
  n = n_subjects, # this is the per arm n
  between = list(group = c("active", "wl")),
  within = list(time = c("T1", "T2", "T3", "T4")),
  mu= df means.
  sd = sd across,
  dv = "score",
  r = correlations across,
  long = TRUE,
  plot = FALSE,
  rep = number sims
 )
 temp results <- lst()
 temp results disp <- lst()
 temp_p_values <- 0
 for(i in 1:n sims){
  temp_results[[i]] <- aov(score~ time + group + time*group , data =
arts on pres sim$data[[i]])
  temp_results_disp[[i]] <-broom::tidy(temp_results[[i]])</pre>
  temp_p_values[i] <- temp_results_disp[[i]]$p.value[3]
 return(temp_p_values)
}
```

```

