# here come the parameters that I will pass to this function
# from https://hqlo.biomedcentral.com/articles/10.1186/1477-7525-10-156
mean T1 <- 43.5 # the biggest trial in that list, the PEIP
sd T1 <- 10.4 # from that trial
d <- -0.5 # stipulated effect size of difference

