## test <- aov(response~factor(drug)+Error(factor(patient)), data = df)
##
##

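### The power simulation names two effect sizes (0.5 and 0.4) and tests a 3-df interaction without a subject error term, not the planned single coefficient b3

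*Protocol*

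**What the plan says.** **Effect size.** The parameter list in the protocol section Target Sample Size per Arm reads "Effect size corresponding to d = 0.5", and the running code agrees in size: "d <- -0.5 # stipulated effect size of difference". The comments that describe the simulation, printed before the function and repeated at the end of the code, say "the treatment group changes to arrive at a d = 0.4" and attribute that value to an advance decision by the investigators.

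**Planned test.** In the Model section, "The inference of interest for the model concerns b3, the interaction term". It is a difference in slopes, judged by t = b3/SE against 1.96. Equation (1) has one treatment-by-time coefficient and shows no subject term.

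**Simulated test.** The code generates four correlated scores per person, labelled T1 to T4 as factor levels, fits "aov(score~ time + group + time*group" and takes the p-value in the third row of the table. The only error stratum in the document is in a commented-out line that refers to a different dataset: "aov(response~factor(drug)+Error(factor(patient)), data = df".

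**Correlation.** The parameter list and the code comment give 0.6; the running line sets 0.5.

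**Occasions.** The simulation has four equally spaced measurements. Frequency of Measurement lists T0 to T3 for adults, with T0 described as demographics before randomisation, and T0, T1 and T3 for children. Design places a two-month break between T3 and T4.

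No resulting n per arm appears in the readable text.

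**The concern.** A simulation supports a power claim only if it uses the intended effect, the intended test and the intended alpha. Here all three are in doubt.

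- Two effect sizes are each presented as the pre-set one. Required n scales with 1/d², so moving from 0.5 to 0.4 multiplies n by (0.5/0.4)² = 1.56.
- A 3-df interaction spreads a linear effect over three degrees of freedom. It is not the test of b3.
- With no subject term, between-person variance stays in the residual against which a within-person contrast is judged. The test is then far stricter than alpha 0.05.

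The errors pull in different directions, so a reader cannot tell what power any given n has for the analysis that will be done.

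**Working it through.** The protocol states no n, so there is no figure to reproduce. The check works out what the printed code would return, then what the planned test would need.

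**Inputs from the protocol.** Power 0.80; two-sided alpha 0.05 (critical value 1.96); equal arms; d = 0.5 or 0.4; r = 0.6 or 0.5; equal SD at all occasions (10.4, set to 1 here because only d matters); control mean flat; active mean moving linearly to d at the last occasion; search grid 20 to 300 per arm in steps of 20. Compound symmetry follows from the single r in the code.

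**1. What the third row is.** With the terms time, group, time × group and n = 100 per arm, a sequential analysis of variance gives 3, 1, 3 and 792 df. Row three is the 3-df interaction, against a residual that still contains between-person variance.

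**2. Null behaviour of the printed test.** The interaction mean square has expectation 1 − r, while the residual is about 1. In large samples the rejection rate is P(χ²₃ > 7.815/(1 − r)):

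- r = 0.5: P(χ²₃ > 15.63) = 0.00135
- r = 0.6: P(χ²₃ > 19.54) = 0.00021

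Monte Carlo (20,000 runs, n = 160) gave 0.0015 and 0.0002. The stated alpha is 0.05.

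**3. Power of the printed test.** The arm differences are δ = (0, d/3, 2d/3, d), so Σ(δ − mean)² = 5d²/9 and λ = (n/2)(5d²/9). Power = P[χ²₃(λ/(1 − r)) > 7.815/(1 − r)].

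| d | r | n per arm for 80% | first passing grid value | power at 160 |
|---|---|---|---|---|
| 0.5 | 0.5 (as coded) | 149.5 | 160 | 0.84 |
| 0.5 | 0.6 | 146.8 | 160 | 0.86 |
| 0.4 | 0.5 | 233.7 | 240 | 0.53 |
| 0.4 | 0.6 | 229.4 | 240 | 0.51 |

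Monte Carlo at r = 0.5 (4,000 runs) gave 0.845 and 0.529 at n = 160, and 0.809 at n = 240 with d = 0.4. The r conflict hardly moves this test: 147 against 150.

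**4. The planned single b3.** Scale time from 0 to 1, so that b3 = d. Let S be the sum of squared centred times: 5/9 for four equally spaced occasions, 1/2 for T1, T2, T3 or for T1 and T3 only. The true SE of b3 is √[2(1 − r)/(nS)].

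- Ordinary residual error (test uses √[2/(nS)]): n = 2(1 − r)[1.96/√(1 − r) + 0.8416]²/(S d²). Four occasions, d = 0.5, r = 0.5: 1 × 3.613²/(0.5556 × 0.25) = 94.0.
- Within-subject error: n = 2(1 − r)(1.96 + 0.8416)²/(S d²). T1 to T3, d = 0.5, r = 0.5: 1 × 7.849/(0.5 × 0.25) = 62.8.

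| test of b3 | d = 0.5 (r 0.6 / 0.5) | d = 0.4 (r 0.6 / 0.5) |
|---|---|---|
| ordinary error, four occasions | 89.4 / 94.0 | 139.8 / 146.9 |
| ordinary error, T1–T3 | 99.4 / 104.5 | 155.3 / 163.2 |
| within-subject error, T1–T3 | 50.2 / 62.8 | 78.5 / 98.1 |

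Monte Carlo at r = 0.5 agrees for the T1–T3 rows: ordinary error 0.794 (n = 104, d = 0.5) and 0.790 (n = 163, d = 0.4); within-subject error 0.811 (n = 63, d = 0.5) and 0.790 (n = 98, d = 0.4). Under the null, the slope test with ordinary error still rejects only 0.56% (r = 0.5) or 0.19% (r = 0.6) of the time; with within-subject error it rejects about 5%.

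**5. Occasions, conditional on what the labels mean** (printed type of test, d = 0.5, r = 0.5). If the labels are the visits, T4 lies after the break and the 12-week comparison ends at T3 with two thirds of d reached: δ = (0, d/3, 2d/3), 2 df, n = 313. If the four occasions are T0 to T3, the code puts a third of the effect at T1, before treatment starts; with no effect until after T1, δ = (0, 0, d/2, d), 3 df, n = 121 instead of 150.

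**The case against.** The strongest reply is that the mistakes largely cancel. The power of 0.53 at 160 per arm belongs to the coded test, which is not the planned one. At the same n and d = 0.4, the single b3 test has power 0.84–0.87 with ordinary error over four occasions, 0.79–0.82 over T1 to T3, and about 0.95–0.98 with within-subject error over T1 to T3. A trial sized from the printed code would therefore be adequate, or nearly so, for b3 even at the smaller effect. This stands, and it is why underpowering is not claimed.

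Three further points carry weight. The 0.4 occurs only in a comment and its verbatim repeat, whereas the parameter list and all code lines use 0.5; still, the comment says 0.4 was the value chosen beforehand, so the intended effect is unclear. The r conflict is negligible for the test as coded. The occasion figures depend on how the labels are read and should not drive the conclusion.

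It can also be said that equation (1) is schematic and that an analysis plan not shown may give the error structure. That is fair for equation (1). It does not rescue the simulation, which is printed in full and omits the term.

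**Conclusion.** The concern holds and should be fixed. The 80% power statement rests on two effect sizes and on a test that is neither the planned one nor run at alpha 0.05.

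With ordinary residual error and the coded four occasions, the document's own conflicts in d, r and type of test span about 89 to 234 per arm. That is the full range across combinations, not uncertainty about any stated n. Adding a subject term lowers the need further, and r then matters: 50 against 63 per arm at d = 0.5 over T1 to T3. For d = 0.5 and r = 0.5, the printed code asks for about 150/63 = 2.4 times what that within-subject b3 test needs.

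The figures assume compound symmetry, equal SDs, equal arms, a linear course to d at the last occasion, no dropout and large-sample approximations. The effect on the trial's actual size cannot be judged, because no target n is visible.

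**What to change.** 1. Choose one d and one r, and use them in the parameter list, comments and code.
2. State which visits the simulated occasions represent. Re-run with the primary visits (T1, T2, T3 for adults; T1 and T3 for children), no arm difference at T1, and d reached at T3.
3. Enter time as numeric and test the single b3 with a subject-level error term, for example a random intercept per participant. Show the same term in equation (1).
4. Confirm that the simulated test rejects in about 5% of null runs.
5. State the resulting n per arm and its power. If recruitment is already fixed, report power at that n for both d = 0.4 and d = 0.5.

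The cost is small: a few changed lines of existing code (means, occasions, time coding, model), a second run for the children's schedule, and corrected text. No new data are needed. The stated n or power may move in either direction.

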# what should matter are
# a) sds which I will keep the same as in baseline
# b) number of measurements, stipulated to be n = 4
# c) number of people, sample size, which I will vary for the simulation
# here comes the actual function
ancova sim func <- function(df means, sd across, n subjects, number sims,
correlations across){
 arts on pres sim <- sim design(
  n = n_subjects, # this is the per arm n
  between = list(group = c("active", "wl")),
  within = list(time = c("T1", "T2", "T3", "T4")),
  mu= df means.
  sd = sd across,
  dv = "score",
  r = correlations across,
  long = TRUE,
  plot = FALSE,
  rep = number sims
 )
 temp results <- lst()
 temp results disp <- lst()
 temp_p_values <- 0
 for(i in 1:n sims){
  temp_results[[i]] <- aov(score~ time + group + time*group , data =
arts on pres sim$data[[i]])
  temp_results_disp[[i]] <-broom::tidy(temp_results[[i]])</pre>
  temp_p_values[i] <- temp_results_disp[[i]]$p.value[3]
 return(temp_p_values)
}
```

```
# here come the parameters that I will pass to this function
# from https://hqlo.biomedcentral.com/articles/10.1186/1477-7525-10-156
mean T1 <- 43.5 # the biggest trial in that list, the PEIP
sd T1 <- 10.4 # from that trial
d <- -0.5 # stipulated effect size of difference
# to derive the mean needed for the final effect size
# cohen d = mean T1-mean T4/sd T1 # using sd T 1 as I stipulated this to be the same
throughout
# which converts to
mean T4 <- mean T1 + d*sd T1
# to create equally spaced value, my idealised decline of values
the treatment means <- seg(mean T1, mean T4, length.out = 4)
# the control means will be the same throughout
the_control_means <- rep(mean_T1, 4)
# investigators assume a correlation between values from each time point r = 0.6
within corr <- 0.5
# now investigators can simulate using faux.
n sims <- 500
# the way I have created the function above, I need to create this dataframe as an obejct for
# the faux function
df_means <-data.frame(T1 = c(the_treatment_means[1], the_control_means[1]),
             T2 = c(the_treatment_means[2], the_control_means[2]),
             T3 = c(the treatment means[3], the control means[3]),
             T4 = c(the_treatment_means[4], the_control_means[4]),
             row.names = c("active", "wl"))
# Now I will loop this function over a number of different sample sizes
# this is the list of sample sizes
n per arm <- seq(20,300, by = 20)
# this is the p-values to extract
p vals <- lst()
p_above_criterion <- 0
for(i in 1:length(n_per_arm)){
p vals[[i]] <- ancova sim func (df means = df means, sd across = sd T1,
          n_subjects = n_per_arm[i] , number_sims = n_sims, correlations_across
          = within corr)
```

```
p above criterion[i] <- sum(p vals[[i]]<0.05)/length(p vals[[i]])</pre>
}
p above criterion
# now I can plot the sample sizes
df to plot <- data.frame(p_above_criterion = p_above_criterion, n_per_arm = n_per_arm)
df to plot %>%
 ggplot(aes(y = p_above_criterion, x = n_per_arm))+
 geom point()+
 geom hline(yintercept = 0.8, colour = "red", linetype = "dashed") +
 scale x continuous("sample size", breaks = n per arm)
# # from https://hqlo.biomedcentral.com/articles/10.1186/1477-7525-10-156
# mean_T1 <- 43.5 # the biggest trial in that list, the PEIP
# sd T1 <- 10.4 # from that trial
# d <- -0.5 # stipulated effect size of difference
## to derive the mean needed for the final effect size
## cohen_d = mean_T1-mean_T4/sd_T1 # using sd_T_1 as I stipulated this to be the same
throughout
## which converts to
# mean T4 <- mean T1 + d*sd T1
## to create equally spaced value, my idealised decline of values
# the_treatment_means <- seq(mean_T1, mean_T4, length.out = 4)
## the control means will be the same throughout
# the control means <- rep(mean T1, 4)
## investigators assume a correlation between values from each time point r = 0.6
# within corr <- 0.6
## now we can simulate using faux.
# n sims <- 50
# n_subj_per_arm <- 100
#
#####this is an example
# arts_on_pres_sim <- sim_design(
\# n = 10, \# this is the per arm n
# between = list(group = c("active", "wl")),
# within = list(time = c("T1", "T2", "T3", "T4")),
```

```
# mu= data.frame(T1 = c(the treatment means[1], the control means[1]),
#
            T2 = c(the treatment means[2], the control means[2]),
            T3 = c(the_treatment_means[3], the_control_means[3]),
#
#
            T4 = c(the treatment means[4], the control means[4]),
# # sd= sd_T1,
# row.names = c("active", "wl")),
\# sd = sd T1,
# dv = "score",
\# r = within corr.
# long = TRUE,
\# rep = 1
#
#)
#
#
##dim(arts on pres sim$data[[1]])
#
## test <- aov(response~factor(drug)+Error(factor(patient)), data = df)
##
##
## test <-aov(score~ time + group + time*group, data = arts_on_pres_sim$data[[1]])
## test <-broom::tidy(test)
# # test$p.value[3]
#
# temp results <- lst()
# temp results disp <- lst()
# temp_p_values <- 0
# for(i in 1:n_sims){
# temp_results[[i]] <- aov(score~ time + group + time*group , data =
arts_on_pres_sim$data[[i]])
# temp_results_disp[[i]] <-broom::tidy(temp_results[[i]])</pre>
# temp_p_values[i] <- temp_results_disp[[i]]$p.value[3]
#
# }
# sum(temp p values<0.05)/length(temp p values)
# create a function for all the above -----
# I will simulate the following
# two groups, treatment and WL control.
# they start off with distributions with the same mean and sd (due to randomisation)
```

- # the WL control stays the same, the treatment group changes to arrive at a d = 0.4, which i
- # what investigators stipulated in advance
- # the shape of the change should not matter that much for this linear model calculation
- # what should matter are
- # a) sds which I will keep the same as in baseline
- # b) number of measurements, stipulated to be n = 4
- # c) number of people, sample size, which I will vary for the simulation

Brief description of tools:

- Patient's personal data and demographics (i.e. name, age, nationality, religion, educational level, marital status, socio-economic characteristics, medical history, mental health problems, medication, therapies).
- The Warwick-Edinburgh Mental Wellbeing Scale (WEMWBS). This tool was developed in order to measure mental wellbeing in the general population by Tennant et al. (2007). It consists of 14 items responding using a 5-point Likert scale from 1 (never) to 5 (all the time). The overall score is calculated by summing the responses for every item without reversing none. The minimum overall score ranges from 14 to 70. Higher scores indicate increased mental wellbeing. The scale has been widely used nationally and internationally for monitoring, evaluating projects and programmes and investigating the determinants of mental wellbeing. An efficient internal consistency was proven using Cronbach's alpha score which was 0.89 for the student sample and 0.91 for the general population sample. Also, test-retest reliability at one week was high (0.83). The Greek validation showed acceptable internal consistency (Cronbach's alpha score 0.90).

The Generalised Anxiety Disorder Assessment (GAD-7) is provided to screen symptom severity for the four most common anxiety disorders (generalized anxiety disorder, panic disorder, social phobia and posttraumatic stress disorder). GAD-7 constructed by Spitzer et al (2006) and validated in Greek by Vogazianos et al (2022). It consists of 7 items. The GAD-7 score is computed by assigning scores of 0, 1, 2, and 3, to the response categories of 'not at all', 'several days', 'more than half the days', and 'nearly every day', respectively, and summing together the scores for the seven questions (scores range from 0 to 21). Higher levels indicate increased anxiety. There are cut-offs for severity of anxiety as: (i) score 0-4: Minimal Anxiety; (ii) score 5-9: Mild Anxiety; (iii) score 10-14: Moderate Anxiety; (iv) score greater than 15: Severe Anxiety. The internal consistency of the GAD-7 was excellent (Cronbach α = 0.92) and testretest reliability was also efficient (intraclass correlation = 0.83) (Spitzer et al., 2006). [Spitzer RL, Kroenke K, Williams JB, et al; A brief measure for assessing generalized anxiety disorder: the GAD-7. Arch Intern Med. 2006 May 22;166(10):1092-7]. [Vogazianos P, Motrico E, Domínguez-Salas S, Christoforou A, Hadjigeorgiou E. Validation of the generalized anxiety disorder screener (GAD-7) in Cypriot pregnant

and postpartum women. BMC Pregnancy Childbirth. 2022 Nov 15;22(1):841. doi: 10.1186/s12884-022-05127-7].

• The Patient Health Questionnaire-9 (PHQ-9) is a questionnaire which measures depression and grade severity of symptoms in general medical and mental health settings using nine DSM-5 criteria for major depression within the last two weeks. PHQ-9 constructed by Kroenke et al. (2001) and validated in Greek by Hyphantis et al. (2011) is using a four-point Likert-type scale. After summing all responses (0=not at all, 3=nearly every day), scores range from 0 to 27, with higher levels indicating increased symptom severity (0–4 no to minimal; 5–9 mild; 10–14 moderate; 15–19 moderately severe; 20–27 severe). The internal reliability of the PHQ-9 was excellent, with a Cronbach's α of 0.89 in the PHQ Primary Care Study (Kroenke et al., 2001) and 0.82 in Greek validation (Hyphantis et al., 2011).


• The Revised UCLA Loneliness Scale-20 (UCLA-20) is a questionnaire which measures level of psychological loneliness experienced by a person. UCLA-20 constructed by Russel et al. (1980) and validated in Greek by Anderson & Malikiosi-Loizos (1992). The internal reliability of the UCLA-20 was excellent, with a Cronbach's α of 0.94 (Russel et al., 1980) and 0.89 in Greek validation (Anderson & Malikiosi-Loizos, 1992). This long scale was shortened to 3 questions (UCLA 3-item Loneliness Scale) in order to be used in large surveys (Hughes et al., 2004). It is using a 3-point Likert-type scale (hard ever, some of the time, often). The scores can be added together to give a range of scores from 3 to 9. Higher scores mean most lonely (worse outcome).

• The Strengths and Difficulties Questionnaire (SDQ) is a brief behavioural screening tool for children and adolescents aged 2-17 years. PHQ-9 constructed by Goodman (2001) and validated in Greek by Gomez et al. (2021) is using a 3-point Likert-type scale ("not true," "somewhat true", "certainly true"). SDQ consists of 25 positive and negative items. These 25 items are divided between 5 scales: (i) emotional symptoms (5 items), (ii) conduct problems (5 items), (iii) hyperactivity/inattention (5 items), (iv) peer relationship problems (5 items), (v) prosocial behaviour (5 items). "Somewhat

true" is always scored as 1 but the scoring of "not true" and "certainly true" varies and score 0 or 2. The total difficulties score is generated by summing the cores form all the scales except the prosocial scale. The final score can be ranged from 0 to 40. Higher scores mean most difficulties (worse outcome). Cronbach's alpha of the original study for all scales ranged from 0.35 to 0.64.

[Goodman R (2001) Psychometric properties of the strengths and difficulties questionnaire. J Am Acad Child & Adolesc Psychiatr 40(11):1337–45]. [Gomez R, Motti-Stefanidi F, Jordan S, Stavropoulos V. Greek Validation of the Factor Structure and Longitudinal Measurement Invariance of the Strengths and Difficulties Questionnaire-Self Report (SDQ-SR): Exploratory Structural Equation Modelling. Child Psychiatry Hum Dev. 2021 Oct;52(5):880-890. doi: 10.1007/s10578-020-01065-7].
